#### **17.4.9 Response to Next Treatment for CLL**

It is hypothesised that patients who had less ibrutinib treatment before progression may have a better response to subsequent treatment, having been less exposed to long periods of prior treatment. Objective response rate is defined as a categorical outcome consisting of whether a participant had PR, SD or PD according to the response criteria defined by the standard 2018 iwCLL criteria (Appendix 1). The best response achieved by a participant at any timepoint will be used to assess the overall response. Again the outcomes CR and CRi will be not considered to avoid needing a bone marrow biopsy, if these are reported they will be summarised and included in any analysis as PR.

For the Clinical Need Cohort this endpoint will be defined similarly.

#### **17.4.10 Resistance Mutation**

The proportion of participants in each arm with a detectable BTK mutation (C481S and variant mutations or an alternative described resistance mutation such as the mutation of PLC- $\gamma$ 2) will be assessed at baseline, 24 months and 48 months for all randomised participants, and at 12, 36 months for those participants in whom a BTK mutation is detected.

#### **17.4.11 Evolution of Resistant Sub-Clones**

The proportion of BTK mutated CLL over time. This will be assessed at baseline and at the timepoints laid out in 13.8.2 by HMDS. If resistant subclones are present, biobank samples will be used to identify the onset of these subclones.

#### **17.4.12 Analysis of the cause of ibrutinib resistance where BTK mutations are not found**

A BTK mutation or alternative resistance mutation is not observed in a significant proportion of participants who develop acquired resistance to ibrutinib. At present the mechanism for such resistance is not clear and the samples taken in this trial will be used to study the mechanism of resistance in these cases.

#### **17.4.13 Identification of predictors for early progression of CLL after pausing ibrutinib**

It is likely that some participants on the intermittent treatment strategy will remain in remission off treatment for a prolonged even indefinite period of time whereas others will progress rapidly after pausing ibrutinib. The level of minimal residual disease is expected to strongly influence the time off treatment. It may also be expected to be influenced by other disease specific factors such as IGHV mutation status. There may also be additional factors that influence treatment interval. All of these will be studied in the trial from samples collected at baseline.

#### **17.4.14 Study of CLL clonal evolution in patients treated with ibrutinib**

It is well recognised that the CLL cells from patients can develop mutations of multiple genes some of which drive resistance and others merely demonstrate clonal evolution. Such clonal evolution within the CLL population is a key driver of resistance to therapies in general and the analysis of this would be expected to shed light on why some patients remain responsive to therapies such as ibrutinib whereas others don't. We intend to study this clonal evolution within the STATIC trial.

#### **17.4.15 Assessment of response to vaccines and on infectious complications**

The rates of infections, in particular of COVID-19 infections, will be assessed in the trial. This will be correlated by vaccination status (unvaccinated, 1 dose of a vaccine, 2 doses etc.). The number of participants who have received at least one dose of a vaccine will be summarised by vaccine.

The serological response to COVID-19 vaccinations will be assessed and the seroconversion rates will be compared between the two arms to assess whether a temporary cessation of ibrutinib improves vaccine response.

# 18 STATISTICAL CONSIDERATIONS

---

## 18.1 Sample Size

As the primary endpoint will be evaluated for the Randomisation Pathway the sample size and recruitment rate calculations are based on participants entering this pathway.

In relapsed/refractory patients, the median PFS on ibrutinib is almost 4 years [7]. In treatment naive patients, the median PFS is estimated to be approximately 10 years [6]. We expect to be able to recruit ~45% of participants from FLAIR and ~55% from relapsed/refractory patients. We assume that PFS will be strongly related to the primary endpoint: time to treatment strategy failure. Assuming exponential distributions leading to a hyperexponential distribution, these medians combine to produce an overall median PFS of 5.84 years. We use PFS here as a surrogate for time-to-treatment strategy failure.

With a one-sided alpha of 2.5%, 80% power and allowing for 5% dropout, to detect a non-inferiority hazard ratio (HR) upper bound of 1.33 would require 379 events (using the continuous treatment arm as the reference). Accounting for those participants who will be lost-to-follow-up 800 patients (approximately 140/year) are planned to be randomised over a 6 year period, with the required number of events expected at approximately 3 years after the close of recruitment.

The highest HR point estimate that would lead to a result of non-inferiority is 1.08, based on a 95% confidence interval of (0.89, 1.33). This corresponds to the intermittent treatment strategy having an 8% extra risk of relapsing, or equivalently a 2.7% decrease in 5-year PFS probabilities (55.2% to 52.5%), with a range of a 9.3% decrease to a 3.3% increase. This reduction in PFS agreed to be clinically acceptable with the National Cancer Research Institute (NCRI) CLL subgroup, because of expected reduction in toxicity, increase in QoL, and the substantial potential for health care resource savings. In addition, there are good salvage therapies on progression, such as venetoclax which is approved for patients failing ibrutinib in the NHS, so a small impact on PFS would not be likely to translate to a difference in overall survival (OS).

We believe it is very likely that the intermittent strategy will actually be superior to continuous treatment in terms of PFS, because the treatment breaks may well delay the time to emergence of drug resistance (18, 19) as well as reducing long-term toxicities (20). If the experimental strategy is actually 5% better, the power increases to 90%.

Considering the number of FLAIR participants taking ibrutinib who are reaching the end of the study, 30 patients are expected to enter the Clinical Need Cohort. This may result in a larger proportion of relapsed/refractory patients being required to reach the Randomisation pathway sample size. However, feasibility and sensitivity analysis has suggested that this remains achievable sample size target that may also shorten the duration of the trial.

## 18.2 Recruitment Rate

To reach the required 800 participants the trial will recruit for a total of 6 years. This requires on average approximately 12 participants per month to be recruited.

### **18.2.1 Recruitment Feasibility Milestone**

To ensure the feasibility of recruitment to the trial, the trial has been designed with a recruitment feasibility milestone incorporated.

A red/ amber/ green decision criteria for continuation will be assessed between months 6 and 18. Recruitment is expected to increase gradually over a 12 month period to a steady-state rate. Our expected recruitment rate is 12 patients per month at the steady-state level, which corresponds to a rate of 0.12 patients/centre/month given that we anticipate running the trial in approximately 100 centres.

The red/ amber/ green decision criteria will be used based on 95% and 80% confidence intervals for this expected recruitment rate over months 6-18.

Applying this criteria:

- If 114 patients were recruited between months 6-18 ( $>0.107$  patients/centre/month), the trial would be deemed to be feasible (green)
- Recruitment of 105-113 patients ( $0.100$ - $0.107$  patients/centre/month) would put us in the amber category
- Lower recruitment would demonstrate that recruitment was infeasible (red)

If recruitment was in the amber target we would explore the reasons for this and take actions, if deemed appropriate. This could include improvements to patient materials, amending eligibility criteria or opening additional centres. If recruitment was in the red category a rescue plan will be put in place following review by the trial independent DMEC and TSC.

# 19 STATISTICAL ANALYSIS

---

## 19.1 General considerations

Statistical analysis is the responsibility of the CTRU statisticians, with the exception of the analysis for cost-effectiveness, which will be undertaken by the Health Economists at the University of Leeds. A full statistical analysis plan will be written before any analysis is undertaken.

For analyses carried out by the CTRU, the analysis plan will be written in accordance with current the CTRU standard operating procedures and will be finalised and agreed by the following people: the trial statistician and supervising statistician, the Chief Investigator and the CTRU Scientific and Project Delivery Leads. Any changes to the finalised analysis plan, and reasons for changes, will be documented.

The analysis population used will depend on the pathway and is detailed below. The intention to treat (ITT) population will include participants according to their randomisation allocation, regardless of eligibility and whether they prematurely discontinued treatment or did not comply with the regimen. The per-protocol (PP) population will exclude individuals who did not uptake their trial treatment or strategy, as well as those who are found to be ineligible following randomisation or any other major protocol violations, as determined by the CI. The safety population will consist of all participants who receive at least one dose of the study treatment on study. The populations for each pathway will be fully defined within the statistical analysis plan (SAP).

## 19.2 Frequency of analysis

### 19.2.1 Interim analyses

An independent data monitoring and ethics committee (DMEC) will be assembled to monitor the data during the trial and will review annual safety data and strategy characteristics (e.g. time spent on treatment breaks) by stratification factor with the intention of detecting major difference in intermittent strategy efficacy. In this event, consideration will be given to the transfer of all high MRD level participants to the Clinical Need Cohort. A planned interim analysis, expected to take place upon half the number of required events occurring in the primary endpoint (190), will be presented to the DMEC. The content of these reports will be fully detailed within the statistical analysis plan (SAP).

The DMEC, in the light of the reports they review and of any advice or evidence they wish to request, will if necessary report to the Trial Steering Committee if there are concerns regarding the safety of the trial treatment.

### 19.2.2 Final analyses

The final analysis will take place upon the trial reaching its specified stopping point, 379 treatment failure events. This is estimated to be approximately 3 years after the close of recruitment.

## 19.3 Primary Endpoint Analysis

The primary endpoint will be assessed on both the PP and the ITT population in the Randomisation Pathway, as recommended (21). In order to reject the null hypothesis that the intermittent strategy is

inferior, we require demonstration of non-inferiority in both the PP and ITT populations. If the results of the analyses are discrepant this will be reported to highlight the inconclusiveness result.

### **19.3.1 Time to Treatment Strategy Failure**

Cox regression analysis will be used to analyse the time to strategy failure accounting for stratification factors (excluding centre), and Kaplan-Meier curves will be presented. The proportional hazards assumptions will be assessed by plotting the hazards over time (i.e., the log cumulative hazard plot). Participants not known to have experienced treatment failure or death at the time of the analysis will be censored at the last date they were known to be alive and not suffering active disease. This comparison will be made against a 2.35% significance level, adjusted to maintain an overall one-sided 2.5% significance level with the included interim analysis of this endpoint. Comparisons will be made against a hazard ratio non-inferiority margin of 1.33, considering the continuous treatment strategy as the reference.

A formal interim analysis on the primary endpoint will be presented to the DMEC when half the number of events (190) have been reported across both treatment arms, with an O'Brien Fleming adjustment used to maintain the overall type I error rate. This is anticipated to be after 5 years of recruitment.

If the upper 95% CI for the observed interim HR is less than the lower bound of our NI margin CI, the trial will be stopped for futility and all participants who are having a treatment break will be able to go back onto therapy. If the lower limit of the 99.5% CI for the HR is higher than the upper bound of our NI margin CI, the trial will be able to report early evidence of non-inferiority. This confidence level corresponds to a significance level of 0.25% for a one-sided test. This value has been calculated using the alpha spending approach with the O'Brien Fleming approximation (22).

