### 8.1 Overall design and plan of the study

The 'Randomisation Pathway' is designed as a prospective, multicentre, open-label, randomised, controlled, 2-arm, parallel-group, non-inferiority study to compare an intermittent treatment strategy (experimental arm) with continuous treatment (control arm) with ibrutinib for patients with CLL who have responded well to treatment with ibrutinib. The primary outcome for this pathway will be time to treatment strategy failure, defined as the first documented instance of active disease as defined by the 2018 iwCLL criteria (Appendix 1) that does not respond to treatment, or death from any cause.

At randomisation previously treated participants will have been receiving ibrutinib as their second- or subsequent-line of therapy for at least the previous 36 months, whilst front-line participants entering from the FLAIR trial will have received 6 years of treatment with ibrutinib. There is no restriction on maximum duration of treatment for the previously treated cohort prior to enrolment. The recruitment period is 6 years, and each participant will be followed up for at least 3 years after randomisation. Participants will receive treatment during the trials 6 year recruitment period and for the 3 years of follow up, meaning that participants will be on the trial for between 3-9 years, depending upon when they enter the trial. 800 patients will be entered into the Randomisation Pathway with the goal of observing 379 treatment failure or death events.

Participants will be randomised to either an intermittent treatment strategy or to continuous therapy. Treatment allocation (1:1) will be by minimisation with a random element incorporating the following three factors: centre, whether or not the participant was previously treated in FLAIR and minimal residual disease (MRD) level at randomisation.

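### The 0.25% interim and 2.35% final levels are not what the named O'Brien-Fleming spending method gives; type I error is still controlled, and 18.1 should say what its 80% power refers to

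*Protocol*

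**What the plan says.** Protocol 19.3.1 plans one formal interim analysis of the primary endpoint at 190 events and a final analysis at 379. The interim uses a 99.5% confidence interval: "This confidence level corresponds to a significance level of 0.25% for a one-sided test". The next sentence says the value was computed by alpha spending with the O'Brien-Fleming approximation. For the final analysis: "This comparison will be made against a 2.35% significance level, adjusted to maintain an overall one-sided 2.5% significance level".

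Protocol 18.1 sizes the trial as follows: "With a one-sided alpha of 2.5%, 80% power and allowing for 5% dropout", and "to detect a non-inferiority hazard ratio (HR) upper bound of 1.33 would require 379 events". It adds: "If the experimental strategy is actually 5% better, the power increases to 90" per cent. It mentions neither the 2.35% level nor a second analysis population.

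Protocol 19.3 sets the success rule: "we require demonstration of non-inferiority in both the PP and ITT populations".

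**The concern.** The protocol fixes two decision thresholds and names the method behind them, so the numbers can be checked. If they do not follow from the method, a statistical analysis plan that implements the named method will contradict the protocol's figures, and one that copies the figures will contradict the named method. The interim level decides whether non-inferiority may be reported early, so the conflict should be settled before the 190-event look.

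The power statement raises a related question. The 80% is quoted for a one-sided 2.5% test, whereas the final test is at 2.35% and must succeed in two populations. A funder or data monitoring committee could take 80% as the chance of success under the rule as written.

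**Working it through.** **Inputs.** From the protocol: overall one-sided alpha 0.025, 379 events and margin 1.33 (18.1); interim at 190 events, levels 0.25% and 2.35% (19.3.1); 1:1 allocation (8.1); success in both ITT and PP (19.3). Assumed: a true hazard ratio of 1.0 under the alternative. The protocol does not write this down, but it reproduces the stated figures. I treat each stated level as the level of a one-sided test against the margin.

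**1. The plan's own figures.** Events = 4(1.960 + 0.842)² / (ln margin)².
- Margin 1.33: 386.0, rounded up to 387. Margin 4/3: 379.4.
- Power with 379 events = Φ(½√379 · ln(margin) − 1.960): 79.3% at 1.33 and 80.0% at 4/3.
- At a true hazard ratio of 0.95 and margin 1.33: 90.6%.

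The 379 events, 80% and 90% all reproduce, with 1.33 apparently a rounding of 4/3.

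**2. Levels from the named method.** The O'Brien-Fleming-type spending function is α(t) = 2[1 − Φ(z₀.₉₈₇₅/√t)], with z₀.₉₈₇₅ = 2.2414.
- t = 0.5: 2.2414/0.7071 = 3.170, so α = 0.153%.
- t = 190/379 = 0.501: α = 0.155%.
- The final nominal level solves P(cross at interim or final) = 0.025 for a bivariate normal pair with correlation √t. The result is 2.45%.

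**3. Could another O'Brien-Fleming form give 0.25% and 2.35%?**

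| Form (t = 0.5) | Interim | Final |
|---|---|---|
| Spending function, one-sided 2.5% | 0.153% | 2.45% |
| Classical O'Brien-Fleming boundary | 0.258% | 2.40% |
| Half of a two-sided 5% spend | 0.279% | 2.39% |
| Protocol | 0.25% | 2.35% |

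None gives the stated pair. With 0.25% kept at the interim, the final level that uses exactly 2.5% is 2.40%. A final level of 2.35% would go with an interim level of about 0.35%.

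**4. Overall error of the stated pair.** With 0.25% and 2.35%, the overall one-sided type I error is 2.447%, below 2.5%.

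**5. Effect on decisions** (margin 1.33).
- Interim, 190 events: the highest passing hazard ratio is 0.885 at 0.25% and 0.865 at 0.15%. The chance of early success at a true hazard ratio of 1.0 is about 20% and 16%.
- Final, 379 events: the highest passing hazard ratio is 1.0845 at 2.35% and 1.0865 at 2.45%.

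**6. Power at the stated final level, one population.** At 2.35%: 78.5% (margin 1.33) or 79.2% (4/3). Counting the interim look: 78.7% or 79.4%. At 2.45% the single-test figure at margin 1.33 is 79.0%.

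**7. Power when ITT and PP must both pass.** Joint power cannot exceed ITT power. Its size needs inputs that the protocol does not give. For illustration, let PP hold a share f of the 379 events, with the same true hazard ratio of 1.0 and correlation √f between the two test statistics. At margin 1.33:

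| PP events lost | At 2.35% | At 2.45% |
|---|---|---|
| 3% | 75.8% | 76.3% |
| 5% | 74.6% | 75.2% |
| 10% | 72.0% | 72.6% |

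**The case against.** The strongest reply is that the stated purpose of the adjustment is met. The pair uses 2.447%, which does not exceed 2.5%, so a reader who infers from the mismatch that type I error is inflated would be wrong. The effect is also small: a difference of 0.002 in the passing hazard ratio at the final, and about half a point of ITT power. The 0.25% is close to the classical boundary, and 19.3.1 also speaks more generally of an O'Brien-Fleming adjustment. All of this stands, and it limits the weight of the point. It does not remove the mismatch, because the protocol states how the 0.25% was calculated and that calculation gives another number.

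A reader may notice that 2.35% equals 2.5% minus 0.15% and conclude that an alpha increment was taken for a nominal level. That is possible, but the protocol shows no such subtraction, so it remains a guess. The mismatch does not depend on it.

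On power, a reader might infer that the 80% is simply wrong. The documents do not support that. The figure reproduces for the calculation that 18.1 describes, and 18.1 does not claim it for the two-population rule. The rounding of 4/3 to 1.33 and the 2.35% level together cost about 1.5 points. Only the two-population rule could produce a larger shortfall. Its direction is certain, but its size rests on figures that the protocol does not give.

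**Conclusion.** The point on the levels holds and needs no assumption beyond the protocol's own inputs. The named spending function gives about 0.15% and 2.45%, and the stated 0.25% and 2.35% match none of the O'Brien-Fleming forms checked. The interim level is about 1.6 times that of the named method, and the final is 0.10 percentage points stricter than that method requires. Overall error is about 2.45%, so this is a mislabelled and slightly inefficient boundary that does not threaten the validity of a positive result.

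The power point is secondary. The 80% is a single-population figure at 2.5%. At the stated final level it is about 78.5% to 79%, assuming a true hazard ratio of 1.0. For the rule that both populations must pass, power is no higher than that. The 72% to 76% range is an illustration that assumes 3% to 10% of events lost from PP, an unchanged hazard ratio and the correlation given above.

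**What to change.** In 19.3.1, choose one of two consistent pairs:
- keep the named spending method and set the interim at one-sided 0.15% (99.7% CI) and the final at 2.45%; or
- keep 0.25% (99.5% CI), name the classical O'Brien-Fleming boundary, and set the final at about 2.40%.

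Leaving 2.35% as a deliberately conservative final level would also be valid, provided the text says so and no longer attributes 0.25% to the spending function.

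In 18.1, say that 80% is the power of a single test in one population at one-sided 2.5%, give the figure at the final level adopted, and state the power for the ITT-and-PP rule under the sponsor's own assumption about PP exclusions.

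The cost is a wording amendment, carried into the statistical analysis plan before the 190-event look, and a somewhat lower stated power. No extra participants are needed for these changes.

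### The interim decision rule in section 19.3.1 is reversed: a clearly better pausing arm is stopped for futility, and a clearly worse one can be reported as early non-inferiority

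*Protocol*

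**What the plan says.** Section 18.1 fixes the scale of the hazard ratio. The design is a one-sided 2.5% test with 80% power, and an "upper bound of 1.33 would require 379 events (using the continuous treatment arm as the reference"). It adds: "The highest HR point estimate that would lead to a result of non-inferiority is 1.08, based on a 95% confidence interval of (0.89, 1.33"), and reads that 1.08 as an 8% higher risk on the intermittent strategy.

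Section 19.3.1 repeats the scale for the analysis: a "hazard ratio non-inferiority margin of 1.33, considering the continuous treatment strategy as the reference". It then sets a formal interim analysis at 190 events, with two rules:

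- **Futility:** "If the upper 95% CI for the observed interim HR is less than the lower bound of our NI margin CI", the trial stops, and participants on a treatment break may resume therapy.
- **Early non-inferiority:** "If the lower limit of the 99.5% CI for the HR is higher than the upper bound of our NI margin CI", the trial may report non-inferiority early. The 99.5% interval is equated with a one-sided level of 0.25%.

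Section 19.3.1 does not say what the NI margin CI is.

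**The concern.** With HR = pausing / continuous, small values favour pausing and large values count against it. An upper limit lying below a bound is therefore good news for pausing, and a lower limit lying above a bound is bad news. Section 19.3.1 attaches the unfavourable decision to the first and the favourable decision to the second.

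This is the only formal stopping rule on the primary endpoint that the protocol gives the data monitoring and ethics committee (DMEC). Followed literally, it gives the wrong recommendation in both directions. The futility stop also carries a treatment consequence for participants on a break, which would follow from data showing that pausing does better. If the committee notices the reversal, it has to devise a rule after seeing unblinded results, which is what pre-specification is meant to prevent.

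**Working it through.** **Inputs**

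- HR = pausing / continuous; margin 1.33 (sections 18.1 and 19.3.1)
- One-sided alpha 2.5%, power 80%, 379 events (section 18.1)
- Interval tied to the margin: (0.89, 1.33) around HR 1.08 (section 18.1)
- Allocation 1:1 (section 8.1)
- Interim at 190 events; 95% interval for futility, 99.5% for early non-inferiority (section 19.3.1)

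**Step 1. Reproduce the plan's own figures.**

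Schoenfeld events = 4(1.960 + 0.842)² / (ln 1.33)² = 386.0, rounded up to 387. The stated 379 is 2.1% lower, and a margin of 4/3 gives 379.4, its likely source.

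At 379 events, SE(log HR) = 2/√379 = 0.1027.

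- Highest HR that passes: 1.33 × exp(−1.96 × 0.1027) = 1.087
- Its lower limit: 1.33 × exp(−2 × 1.96 × 0.1027) = 0.889

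These agree with the stated 1.08 and (0.89, 1.33). So the sample size uses the stated scale, with non-inferiority judged by the upper limit against 1.33.

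**Step 2. Interim precision.**

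SE = 2/√190 = 0.1451. Half-widths on the log scale are 1.960 × 0.1451 = 0.284 (95%) and 2.807 × 0.1451 = 0.407 (99.5%).

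**Step 3. Thresholds as written**, reading the NI margin CI as (0.89, 1.33).

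- Futility: observed HR < 0.89 × exp(−0.284) = 0.670
- Early non-inferiority: observed HR > 1.33 × exp(0.407) = 2.00

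**Step 4. Thresholds with the directions corrected.**

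- Early non-inferiority (upper 99.5% limit < 1.33): observed HR < 1.33 × exp(−0.407) = 0.885
- Inferiority (lower 95% limit > 1.33): observed HR > 1.33 × exp(0.284) = 1.77

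**Step 5. Chance of each decision**, from Φ((ln threshold − ln true HR)/0.1451) or its complement.

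| True HR | As written: futility | As written: early NI | Corrected: early NI | Corrected: lower limit > 1.33 |
|---|---|---|---|---|
| 0.60 | 77.6% | 0 | 99.6% | 0 |
| 0.70 | 38% | 0 | 95% | 0 |
| 0.95 | 0.8% | 0 | 31.3% | 0 |
| 1.00 | 0.3% | 0 | 20.0% | 0 |
| 1.33 | 0 | 0.25% | 0.25% | 2.5% |
| 1.75 | 0 | 18.0% | 0 | 47.3% |
| 2.00 | 0 | 50.2% | 0 | 80.3% |

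The corrected early rule has a 0.25% error rate at the margin, the one-sided level that section 19.3.1 states.

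**Step 6. Two worked results.**

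- Observed HR 0.60: the 95% CI is 0.45 to 0.80. The upper limit is below 0.89, so the trial stops for futility, although the 99.5% CI of 0.40 to 0.90 lies wholly below 1.33.
- Observed HR 2.10: the 99.5% CI is 1.40 to 3.16. The lower limit is above 1.33, so early non-inferiority may be reported, although the whole interval lies beyond the margin.

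**Step 7. Other readings.**

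- *The NI margin CI is the single value 1.33.* Futility fires at an observed HR below 1.33 × exp(−0.284) = 1.00, about a 50% chance when the arms are equal. The early non-inferiority threshold stays at 2.00. Both still point the wrong way.
- *The HR is inverted (continuous / pausing), and the interval with it*, to (1/1.33, 1/0.89) = (0.75, 1.12). Futility (upper limit < 0.75) is then correctly directed and is the same as a lower limit above 1.33 on the stated scale. Early non-inferiority (lower limit > 1.12) equals an upper limit below 0.89 on the stated scale. That demands superiority, at an observed HR below 0.89 × exp(−0.407) = 0.592.
- *The HR is inverted but the interval is left at (0.89, 1.33).* Early non-inferiority needs a lower limit above 1.33, again a superiority claim; the margin on that scale is 0.75.

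**The case against.** The strongest defence is a single drafting slip. If the sentences were written with the HR inverted and the interval inverted too, the direction of both makes sense and the futility rule is exactly right. That may well explain the error, but it does not remove it. Section 19.3.1 names continuous treatment as the reference in the same section, and even on that reading the early rule asks for superiority rather than non-inferiority.

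Four further points stand as limits on the finding.

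- The 0.67 threshold and the 38% depend on taking the undefined NI margin CI to be (0.89, 1.33). The 2.00 threshold does not.
- The DMEC has other routes to act: the annual safety and strategy data in section 19.2.1, the resistance endpoints in sections 19.4.9 and 19.4.10, the value-of-information estimates in section 19.4.3, and its power in Appendix 10 to recommend closure. It would probably question an HR of 2.1 labelled non-inferior.
- True HRs of 0.70 and 2.0 are far from the design values of 1.0 and 5% better. Near those values neither written rule fires often; the realistic loss is that the intended early look for non-inferiority does not exist.
- Section 19.2.1 leaves the content of the DMEC reports to the SAP. The decision thresholds, however, are fixed in the protocol, so a correct SAP would contradict it.

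**Conclusion.** The concern holds. On the protocol's own scale both interim inequalities are reversed, and no other section corrects them. The final-analysis comparison is correctly directed, so the error is confined to these two sentences.

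As written, futility fires on strong evidence for pausing (observed HR below 0.67, or below 1.00 on the single-value reading). Early non-inferiority fires only on proof of inferiority (observed HR above 2.00). The 20% chance of a valid early non-inferiority result at true HR 1.0, and 31% at 0.95, is lost. The figures assume 1:1 allocation, exactly 190 events and a normal approximation to log HR; the reversal itself depends on none of these. It must be corrected before the interim analysis.

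**What to change.** Replace both sentences in section 19.3.1, stating HR as pausing versus continuous:

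- **Early non-inferiority:** the upper limit of the 99.5% CI is below 1.33.
- **Inferiority or futility:** the lower limit of the 95% CI is above 1.33. This mirrors the rule apparently intended. It fires only at an observed HR above 1.77, so it is an inferiority rule and weak as a futility rule. If the sponsor wants a more sensitive non-binding futility bound, it should be stated as an HR in this direction.

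Delete the term NI margin CI and name the number used. Simply exchanging the two consequences is not enough, because early non-inferiority would then require an upper limit below 0.89 rather than below 1.33. The sponsor should confirm the intended bounds and check that the treatment consequence attached to the futility stop still matches the corrected rule.

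The cost is a protocol wording amendment, with the same change in the SAP and DMEC charter if they repeat the rule; neither was available to check. Sample size, the interim level and the timing of the analysis do not change.
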